2.5.1.2. Ranked Secondary efficacy endpoints

Ranked secondary efficacy endpoints (in the order of the endpoints to be tested) are:

- Change from baseline to Month 6 in DYS (VRS)
- Change from baseline to Month 6 in NMPP (VRS)
- Change from baseline to Month 6 in dyschezia (Numeric Rating Scale NRS)
- Change from baseline to Month 6 in overall pelvic pain (NRS)
- Change from baseline to Month 6 in the interference of pain with the ability to perform daily activities, measured using the pain dimension of the Endometriosis Health Profile-30 (EHP-30)
- Change from baseline to Month 6 in dyspareunia (VRS)
- No analgesics use for EAP during the preceding 4-week period at Month 6
- No opiate use for EAP during the preceding 4-week period at Month 6

Additional details on ranked secondary endpoints and analyses are provided in Section 4.6.

2.5.1.3. Additional secondary efficacy endpoints

Additional secondary efficacy endpoints include:

- Clinically meaningful reduction at scheduled visits other than Month 3 for DYS and NMPP
- Change from baseline to each scheduled assessment in the mean pelvic pain scores for DYS, NMPP and overall pelvic pain, during the previous 4-week period assessed on the NRS and VRS

Sponsor:	ObsEva				
Protocol:	18-OBE2109-003				
Document Version No.:	V5.0	Document Date:	13-JUN-2022		

- Change from baseline to each scheduled assessment in the number of days with moderate to severe pelvic pain during the previous 4-week period assessed on the VRS
- Change from baseline to each scheduled assessment in the mean worst pelvic pain score defined as the mean of the 5 highest daily pain scores reported during the previous 4-week period assessed on the NRS
- Change from baseline to each scheduled assessment in the mean of daily dyspareunia scores reported during the previous 4-week period on the dyspareunia VRS
- Change from baseline to each scheduled assessment in the mean of daily dyschezia scores reported during the previous 4-week period assessed on the dyschezia NRS
- Change from baseline to each scheduled assessment in non-opioid, opioid and combined analgesic use for EAP during the previous 4-week period based on pill count in the eDiary
- Change from baseline to each scheduled assessment in opioid analgesic use for EAP as reported in the eDiary during the previous 4-week period based on morphine milligram equivalent (MME)
- Change from baseline to each scheduled assessment in the number of days of analgesic use (including any class) for EAP during the previous 4-week period as assessed in the eDiary
- Change from baseline to each scheduled assessment in the number of days of opioid analgesic use for EAP during the previous 4-week period as assessed in the eDiary
- Change from baseline to each scheduled assessment in the number of pelvic pain-free days (assessed on the VRS) during the previous 4-week period
- Change from baseline to each scheduled assessment in ability to perform daily activities during the previous 4-week period, as assessed in the eDiary (daily function NRS)
- Change from baseline to each scheduled assessment in the number of days with no difficulty in doing daily activities due to EAP during the previous 4-week period as assessed in the eDiary (daily function NRS)
- Change from baseline to each scheduled assessment in the number of days when dyspareunia was a problem during the previous 4-week period (including days when sexual intercourse was avoided because of anticipation of pain) as assessed on the dyspareunia VRS
- Change from baseline to each scheduled assessment in the number of days when sexual intercourse was avoided because of anticipation of pain during the previous 4-week period as assessed on the dyspareunia VRS
- Change from baseline to each scheduled assessment in the number of days with uterine bleeding (including spotting) during the previous 4-week period measured by eDiary

Sponsor:	ObsEva		
Protocol:	18-OBE2109-003		
Document Version No.:	V5.0	Document Date:	13-JUN-2022

- Change from baseline to each scheduled assessment in the number of days when school or work was missed due to EAP in the previous 4-week period as reported in the eDiary
- Change from baseline to each scheduled assessment in the number of days when the subject had to go to bed or lie down due to EAP in the previous 4-week period as reported in the eDiary
- Change from baseline to each scheduled assessment in the Pain, Control and powerlessness, Emotional well-being, Social support, Self-image dimensions and the Modular sexual relationship questionnaire of EHP-30 scores
- Change from baseline to each scheduled assessment in the Health-Related Productivity Questionnaire (HRPQ) scores
- Number of non-study endometriosis related health visits, number of days in hospital and type of procedures performed based on Health Resource Utilization Questionnaire (HRUQ) at each scheduled assessment
- Change from baseline to each scheduled assessment in the Physician/Subject Surgery Intention Question (PSIQ/SSIQ)
- Change from baseline to each scheduled assessment in the PROMIS Fatigue Short Form 6a
- Change from baseline to each scheduled assessment in the EuroQoL 5-Dimension 5-Level (EQ-5D-5L) questionnaire
- Response at each scheduled assessment according to Patient Global Impression of Change (PGIC) (and Post-treatment Patient Global Impression of Change, PPGIC)
- Change from baseline to each scheduled assessment in the monthly PGIS (mPGIS) score

Additional details on secondary endpoints and analyses are provided in Section 4.6.

2.5.2. Pharmacokinetic Variables

PK blood samples will be collected from each subject for determining linzagolix and KP017 plasma levels.

On Day 1, blood samples for PK assessment will be taken at least 1.5 h post-first dose.

During the treatment period, on days of site visits (Months 1, 2, 3, 4, 5 and 6), the subject will be asked to take the dose of IMP at site, after a pre-dose PK sampling. The approximate time of dose administration on the four previous days and time of PK sampling will be recorded in the eCRF.

Pharmacokinetic analyses will be considered exploratory. Analyses are described in Section 4.7.

CRS-BS-TP-000005 V 1.0

Sponsor:	ObsEva		
Protocol:	18-OBE2109-003		
Document Version No.:	V5.0	Document Date:	13-JUN-2022

2.5.3. Safety Variables

Safety endpoints include:

- Change from baseline to each scheduled assessment in BMD measured by DXA of lumbar spine (L1-L4), femoral neck, and total hip
- Incidence and severity of treatment emergent adverse events (TEAEs)
- Incidence and severity of hypoestrogenic TEAEs (hot flush)
- Time to the first post-treatment menses
- Changes in clinical laboratory assessments (hematology, biochemistry, coagulation parameters, hormones, lipids and urinalysis) from baseline to each scheduled assessment
- Any pathological changes from baseline in the endometrium as assessed by histology from endometrial biopsies
- Changes from baseline to each scheduled assessment in any other safety parameter including weight, vital signs, ECG, gynecological assessments and endometrial thickness

Safety analyses are described in Section 4.8.

2.5.4. Exploratory Variables

Exploratory endpoints include:

- Change from baseline in bone turnover markers at each scheduled assessment.

Exploratory analyses are detailed in Section 4.9.

Sponsor:	ObsEva		
Protocol:	18-OBE2109-003		
Document Version No.:	V5.0	Document Date:	13-JUN-2022

3. SUBJECT POPULATIONS

3.1. Analyses Sets Definitions

The following data sets will be used for the statistical analysis:

Screened Set: All screened subjects.

Randomized Set: All randomized subjects.

Safety Set (SAF): All randomized subjects who received at least one dose of double-blind study drug irrespective of the treatment received. Subjects will be analyzed according to treatment received.

Full Analysis Set (FAS): All randomized subjects who received at least one dose of double-blind study drug irrespective of the treatment received. This is the same as the Safety Set, but for the FAS, subjects will be analyzed according to randomized treatment.

Threshold Analysis Set: All subjects from the FAS with any anchor data at both Baseline and Month 3 or early discontinuation visit, or available Month 3 or early discontinuation visit PGIC data only.

Anchor data for the Threshold Analysis Set includes monthly Patient Global Impression of Severity (mPGIS), mPGIC, monthly DYS, monthly NMPP.

M6 Threshold Analysis Set: All subjects from the FAS with any anchor data at both Baseline and Month 6 or early discontinuation visit, or only available Month 6 or early discontinuation visit PGIC data.

Anchor data for Month 6 include monthly Patient Global Impression of Severity (mPGIS), mPGIC, monthly DYS, monthly NMPP, monthly dyschezia, monthly overall pelvic pain, monthly difficulty in daily activities, and monthly dyspareunia.

Per Protocol (PP) Set: All randomized subjects who completed the six months of treatment excluding those identified as having major protocol deviations that could potentially affect the efficacy assessments up to Month 6. Subjects will be analyzed according to randomized treatment.

Follow-up (FU) Set: All randomized subjects who completed the six months of treatment or discontinued treatment between Month 3 and Month 6 and entered the drug free follow-up period. Subjects will be analyzed according to randomized treatment.

Subjects who entered the drug free follow-up period are subjects eligible for the 6-month treatment free follow-up and with any data post month 6 or post treatment discontinuation.

Follow-up Safety Set (FU SAF): All randomized subjects who completed the six months of treatment or discontinued treatment between Month 3 and Month 6, and entered the drug free follow-up period. Subjects will be analyzed according to treatment received.

Sponsor:	ObsEva		
Protocol:	18-OBE2109-003		
Document Version No.:	V5.0	Document Date:	13-JUN-2022

Pharmacokinetic (PK) Set: all subjects who received active study medication, had no major protocol deviations impacting PK evaluation and with available PK data.

In general, analyses of efficacy will be conducted using the FAS, PP and FU sets, analyses of safety will be conducted using the Safety Set and FU SAF, and analyses of PK will be conducted using the PK Set.

The actual treatment will be derived as follows, based on daily e-diary IMP intake data:

Subjects received a different kit of active linzagolix or placebo for each month, and a different kit for addback or placebo for each 3-month period.

The number of days with one pink tablet, one grey tablet and one red capsule taken based on e-diary IMP intake data for each treatment will be computed. Data from "Today" will be used primarily. If data from today is missing, data from "Yesterday" of the following day will be considered. If the e-diary is not completed for a day (neither "Today" nor "Yesterday" of following day), it will be assumed that no intake of drug was taken on that day.

Further rules are as follows:

- Treatment administration errors:
 - If a subject received placebo with placebo ABT in more than 50% of days, then the actual treatment group will be placebo with placebo ABT.
 - Otherwise, the active treatment group (combined with add-back or placebo add-back) with the most days taken will be assigned.
 - If the number of days is equal for two treatments groups containing active treatment then LGX 200 mg with ABT will be assigned.
- If a subject discontinued, only data received up to discontinuation will be used.
- It is possible that the derived actual treatment group does not correspond to any of the planned treatment groups. In that case actual treatment group will be assigned to the planned treatment group with same dose of active treatment. Example: LGX 75mg with ABT will be assigned to LGX 75mg with placebo ABT; LGX 200mg with placebo ABT will be assigned to LGX 200mg with ABT. A listing with such cases will be provided.

3.2. **Protocol Violations**

A protocol deviation is any noncompliance with the clinical trial protocol or International Conference on Harmonization Good Clinical Practice (ICH GCP) requirements. It is the responsibility of the site investigator to use continuous vigilance to identify and report deviations. All deviations must be addressed in study source documents and reported to the reviewing IRB/IEC per their policies. The site investigator is responsible for knowing and adhering to the reviewing IRB/IEC requirements.

Sponsor:	ObsEva		
Protocol:	18-OBE2109-003		
Document Version No.:	V5.0	Document Date:	13-JUN-2022

All Protocol Deviations will be reported to the Sponsor and documented in the monitoring report. These will be classified as minor or major based on their effect on the right, safety or well-being of the subjects and/or the quality and integrity of the data, and the final rating of all deviations will be confirmed prior to database lock. The final protocol deviation file (formatted as a Microsoft Excel file) will be provided to Cytel.

Major protocol deviations will be summarized by category (if available) and by treatment group for the FAS population.

Major deviations that could potentially affect the efficacy assessments up to Month 6 and thus may exclude subjects from the PP Set may include:

- Non-compliance with inclusion criteria 3; 6; 8
- Non-compliance with exclusion criteria 2 to 10 inclusive; 12; 13; 17; 19; 20; 21; 23; 24; 25
- Non-compliance with study treatment: threshold to be defined during blinded data review meeting (e.g. IMP compliance in tablets <60% for Day1-Month 6)
- IP Dispensing error;
- Unauthorised prior or concomitant therapy;
- M3 and/or M6 Visits performed outside the +/-14 days of the theoretical visit date;
- Randomisation code broken;

All protocol deviations will be presented in the data listings.

Sponsor:	ObsEva		
Protocol:	18-OBE2109-003		
Document Version No.:	V5.0	Document Date:	13-JUN-2022

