2. STUDY DESIGN

2.1. Synopsis of Study Design

This is a prospective, randomized, double-blind, placebo-controlled study to demonstrate the efficacy and safety of linzagolix administered orally once daily at doses of 75 mg alone and 200 mg in combination with low dose ABT (E2 1 mg/NETA 0.5 mg) versus placebo in the management of moderate to severe EAP in women with surgically confirmed endometriosis.

The study starts with an approximately 3-month screening period during which subjects will receive no study drug. Eligibility will be confirmed based on data collected during the screening period. After randomization, a 6-month Treatment Period will follow. Subjects will be randomized to one of the three treatment groups:

1. Linzagolix 75 mg

- 2. Linzagolix 200 mg combined with ABT
- 3. Placebo

Randomization will be conducted via an interactive web response system (IWRS) in a 1:1:1 ratio. There will be no stratification.

At 6 months, BMD change will be assessed via DXA measurement. Eligible subjects who have completed the 6-month treatment period may enter a separate extension study for 6 additional months of active treatment (no placebo control). In this extension study, subjects who previously received placebo will be randomly switched to one of the two active treatments (75 mg alone or 200 mg + ABT). Subjects who received active treatment will continue with the same treatment.

Subjects who decline to participate to or do not qualify for the extension study and who were exposed to at least 3 months of treatment will enter a 6-month drug-free follow-up. At the end of the 6-month follow-up period, subjects with a BMD decrease from baseline of >1.5% for lumbar spine and >2.5% for total hip will have an additional DXA scan 6 months later. Subjects who discontinue treatment prior to Month 3 will not enter the follow-up period.

[figure not shown]
The main analysis will be performed after 6 months of treatment and will include all of the subjects' data up to Month 6. The primary endpoint analysis will be based on subjects' data up to Month 3.

The study will last on average 15 months for each patient; 3-month Screening Period, 6-month Treatment Period and 6-month Follow-up (with 1 month being defined as 28 days/4 weeks). This estimated duration excludes any washout period.

Sponsor:	ObsEva						
Protocol:	18-OBE2109-00	18-OBE2109-003					
Document Version No.:	V5.0	Document Date:	13-JUN-2022				

A schematic of the study design is shown in Figure 1.

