4.6.2.1.2. Primary Efficacy Analysis

The primary efficacy analysis will be conducted using the FAS.

The analysis of each co-primary endpoint will be conducted using a logistic regression model, with treatment group as the main effect (three values) and including the baseline pain score as a covariate. Individual linzagolix versus placebo treatment group comparisons will be made using the same logistic regression model. Estimated odds-ratios and 97.5% intervals of proportions of responders of linzagolix treatment groups versus placebo will be presented, along with Bonferroni corrected p-values. Estimates of proportions of responders with 95% confidence intervals will be presented as well, estimated at the overall mean baseline pain score.

SAS Code (may be updated at analysis stage to fit the data):

```
PROC LOGISTIC data=dataset order=internal;
Class treatment(ref=placebo) / param=glm ;
Model resp(event= "Yes")= treatment base_pain /alpha=0.05;
Oddsratio treatment ;
Lsmeans treatment / ilink exp cl alpha=0.05 at means diffs=control('1')
adjust=bon;
Ods output OddsRatiosWald=or ModelANOVA=ma ParameterEstimates=pe
lsmeans=lsm diffs=diffs;
```

Run;

In addition, the mean pelvic pain scores for DYS and NMPP and change from baseline for the last 28 days prior to Month 3 or the last 28 days of treatment (or less) for subjects who discontinued will be summarized as continuous variables by treatment group. Cumulative distribution functions (CDF) for change from baseline at Month 3 for DYS and NMPP will be provided, with separate lines for each treatment group. The x-axis will present the different values for the DYS or NMPP change from baseline, and the y-axis will present the proportion of subjects reaching each value of change. Vertical lines of the relevant MCT thresholds obtained at the Month 3 responder threshold analysis will be displayed on the plots.

The number and percentage of subjects with:

- Reduction of X for DYS,
- Reduction of X for NMPP,

Sponsor:	ObsEva		
Protocol:	18-OBE2109-003		
Document Version No.:	V5.0 Document Date: 13-JUN-2022		

- Stable or decreased use of analgesics for EAP during bleeding days, during non-bleeding days, and overall,
- Reduction of X for DYS and stable or decreased use of analgesics for EAP (during bleeding days),
- Reduction of X for NMPP and stable or decreased use of analgesics for EAP (during non-bleeding days),

will be presented.

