4.6.2.3. Per Protocol Analysis

The primary analysis as described in Section 4.6.2.1.2 will be repeated using the Per Protocol Set.

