4.6.5. Additional Efficacy Analyses

4.6.5.1. Clinically meaningful reduction at Month 3 for the two co-primary endpoints with

Sponsor:	ObsEva		
Protocol:	18-OBE2109-003		
Document Version No.:	V5.0	Document Date:	13-JUN-2022

discontinued subjects considered as non-responders

A supportive analysis of the co-primary endpoint analysis will be conducted that considers all subjects who prematurely discontinue the study treatment before the Month 3 visit as non-responders. These are composite endpoints that estimate the proportion of subjects with clinically meaningful reduction in pain, a stable or decreased use of rescue medication, and who complete 3 months of treatment. The same analyses as described in Section 4.6.2.1.2 will be performed, i.e., using a composite strategy for discontinuation as opposed to a while on treatment strategy used for the primary estimand.

The analysis will be performed on the Full Analysis Set and the Per Protocol Set.

4.6.5.2. Clinically meaningful reduction at Month 3 for the two co-primary endpoints with multiple imputation approach for subjects who discontinued the study early

As supportive analysis of the co-primary endpoint analysis, in order to estimate the effect of treatment policy, a reference based multiple imputation approach will be used for the co-primary endpoints for subjects who discontinue the study early, under the assumption that the efficacy of the linzagolix treated subjects gradually transitions to that observed in the placebo subjects, i.e., using a treatment policy strategy for discontinuation as opposed to a while on treatment strategy used for the primary estimand.

Details on multiple imputation methodology are described in section 4.2.8.

DYS and NMPP mean scores changes, and ibuprofen and analgesic use (pill counts) will be simultaneously imputed using multivariate imputation by a fully conditional specification method, with 20 burn-in iterations before each imputation. The predictive mean matching method for continuous variables will be used where the imputed values will be randomly taken from the 5 closest observed values whose predicted values are closest to the predicted value for the missing value from the simulated imputation model. The imputation model will include baseline value as a covariate. Following imputation, the corresponding binary endpoints of response for DYS, NMPP including use of analgesics, will be computed.

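### The Per Protocol repeat of the Month 3 co-primary analysis admits only subjects who completed six months of treatment, and the Per Protocol run of SAP 4.6.5.1 duplicates it exactly

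*SAP*

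**What the plan says.** The primary endpoint has a Month 3 horizon. SAP 2.1 states: "The primary endpoint analysis will be based on subjects' data up to Month 3". SAP 4.6.2.1.2 fixes the analysis set: "The primary efficacy analysis will be conducted using the FAS".

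The only PP set, in SAP 3.1 and in the same terms in Protocol 13.4, is "All randomized subjects who completed the six months of treatment excluding those identified as having major protocol deviations", the deviations being those "that could potentially affect the efficacy assessments up to Month 6". SAP 3.2 then lists deviations that may lead to exclusion. Two of them can arise wholly after Month 3: low compliance, illustrated as "IMP compliance in tablets <60% for Day1-Month 6" with the threshold left to blinded review, and "M3 and/or M6 Visits performed outside the +/-14 days of the theoretical visit date".

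Two PP analyses of the co-primaries follow:

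- SAP 4.6.2.3: "The primary analysis as described in Section 4.6.2.1.2 will be repeated using the Per Protocol Set".
- SAP 4.6.5.1 counts anyone who stops treatment before the Month 3 visit as a non-responder, keeps the primary model, and adds: "The analysis will be performed on the Full Analysis Set and the Per Protocol Set".

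SAP 4.6 repeats the ranked secondary endpoints, all at Month 6, on the same PP set.

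**The concern.** A PP analysis is normally read as the effect among subjects who followed the protocol for as long as the endpoint required. Here the requirement runs three months longer. A subject who took her treatment, completed her diary to Month 3 and was withdrawn in Month 5 under the liver or ECG stopping rule followed the protocol throughout. She still leaves the PP analysis of an outcome that was already fixed.

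Stopping between Months 3 and 6 may reflect poor pain control, tolerability or a safety rule, and these may differ by arm. If they do, the PP odds ratio compares groups filtered on something that happened after the endpoint. Agreement or disagreement with the FAS result then says less about the effect of deviations than a reader would suppose.

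The second matter is one of reporting. Two PP tables with different titles will carry identical numbers, and a reader could count them as two supportive results.

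**Working it through.** **Inputs (SAP 4.1).** 150 subjects per arm. Each dose is tested at two-sided 0.05/2 = 0.025. DYS response is 14.6% on placebo, 48.6% on 75 mg and 64.7% on 200 mg. NMPP response is 18.8% on placebo and 42.1% on active. No rate of loss between Months 3 and 6 is given by arm or by response, so every loss rate below is an assumption. The odds ratios are crude; the planned model also adjusts for baseline pain.

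**1. The plan's own power.** For NMPP, with pooled variance, the mean proportion is 0.3045 and the critical value is 2.241:

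[0.233 × √150 − 2.241 × √(2 × 0.3045 × 0.6955)] / √(0.188 × 0.812 + 0.421 × 0.579) = (2.854 − 1.459)/0.630 = 2.22, a power of 98.7%.

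DYS power exceeds 99.99% for both doses, so joint power is 98.7%. The stated figure of more than 95% is reproduced. If the PP set lost 10%, 20% or 30% of each arm (135, 120 or 105 left), joint power would be 97.6%, 95.9% or 92.9%. Power is not the issue.

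**2. Effect of selection on the odds ratio.** Let a be the fraction of Month 3 responders lost after Month 3 and b the fraction of non-responders, with subscript 1 for active and 0 for placebo. Retained odds of response are p(1 − a)/[(1 − p)(1 − b)], so

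PP odds ratio = true odds ratio × [(1 − a₁)/(1 − b₁)] ÷ [(1 − a₀)/(1 − b₀)].

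The odds ratio moves only if the ratio (1 − a)/(1 − b) differs between arms.

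*DYS, all late leavers non-responders: 10% of placebo and 5% of active subjects.*

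- Rates become 0.146/0.90 = 16.2% and 0.486/0.95 = 51.2%.
- 75 mg odds ratio before: (0.486/0.514)/(0.146/0.854) = 5.53. After: (0.486/0.464)/(0.146/0.754) = 5.41.
- 200 mg odds ratio before: (0.647/0.353)/(0.146/0.854) = 10.7. After: (0.647/0.303)/(0.146/0.754) = 11.0.
- The shifts are small because the loss among non-responders is similar across arms: 0.10/0.854 = 11.7% on placebo, 0.05/0.514 = 9.7% on 75 mg and 0.05/0.353 = 14.2% on 200 mg.

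*NMPP, true odds ratio (0.421/0.579)/(0.188/0.812) = 3.14.*

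| Assumed loss, Month 3 to 6 | PP rates, placebo v active | PP odds ratio | If the true odds ratio is 1 |
|---|---|---|---|
| 5% of responders, 15% of non-responders, both arms | 20.6% v 44.8% | 3.14 | 1.00 |
| 20% of placebo non-responders, 5% of everyone else | 21.6% v 42.1% | 3.14 ÷ (0.95/0.80) = 2.64 | 0.84 |
| 20% of active non-responders, 5% of everyone else | 18.8% v 46.3% | 3.14 × (0.95/0.80) = 3.73 | 1.19 |

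**3. The duplicate.** Every PP member completed six months, so none stopped before Month 3. The 4.6.5.1 rule therefore changes no PP response, and with the same model and set the output equals that of 4.6.2.3. In 200 simulated trials of 450 subjects it recoded no PP subject. On the FAS it recoded about 15 per trial, assuming 10% stop before Month 3. The rule does work on the FAS.

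**The case against.** The case for leaving the plan alone has weight.

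- **No claim rests on the PP set.** The co-primaries are tested on the FAS, and the PP analyses play no part in the multiplicity scheme. This stands.
- **Robustness to discontinuation is covered elsewhere.** The non-responder composite (4.6.5.1) and the reference-based multiple imputation (4.6.5.2) are both run on the FAS, without selection on Month 6 completion. This also stands.
- **One set is a disclosed choice that suits the Month 6 endpoints.** That is true of the ranked secondaries, but neither document gives a reason for applying it to a Month 3 endpoint. SAP 3.1 itself defines separate Month 3 and Month 6 threshold analysis sets.
- **Any PP set selects on events after randomization.** So would a Month 3 version. The difference is that the present set also selects on events after the endpoint, and that part can be avoided.
- **The duplicate table biases nothing.** Agreed; it is redundant, and the risk is misreading.

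A reader might go further and infer that the PP estimate is biased, perhaps in favor of linzagolix. The documents do not support that. They give no late loss by arm and response, the odds ratio is unchanged when loss depends on response equally in both arms, and the direction can go either way. Nor does every Month 6 deviation exclude a subject: SAP 3.2 lists those exclusions as possibilities. Only the completion requirement is certain.

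**Conclusion.** Both parts hold, in limited form. Membership of the set used for the PP repeat of the Month 3 co-primaries depends on what happens after Month 3: always through the completion requirement, and possibly through Month 6 visit timing or later compliance. The supportive odds ratio can therefore be biased in either direction, provided late loss depends jointly on arm and response. The size cannot be known from the plan. It may be trivial, as in the DYS illustration, or about 16% down or 19% up on the odds ratio under the assumed 20% against 5% loss. The duplication needs no assumption; it follows from the definitions. It would be wrong to read either point as a threat to the primary conclusion. The change is worth making because the selection serves no purpose for a Month 3 endpoint and is cheap to remove.

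**What to change.** For SAP 4.6.2.3, define a Month 3 PP set: subjects who completed treatment to the Month 3 visit and had no major deviation affecting efficacy up to Month 3. Apply the compliance threshold over Day 1 to Month 3, use only the Month 3 visit window, and impose no Month 6 requirement. This settles how earlier discontinuers are handled: they are outside the set, so a PP run of 4.6.5.1 would still be redundant. Run 4.6.5.1 on the FAS only. Keep the six-month PP set for the Month 6 ranked endpoints.

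The cost is one more set definition and a blinded review of deviations and compliance to Month 3. SAP 3.2 does not say that deviations are dated, so this needs checking. SAP V5.0 already reports thresholds derived at the Month 6 database lock (4.6.1.4). A set added after unblinding should be labeled post hoc. If no set is added, the report should at least state that PP membership depends on completing Month 6 and that the two PP tables are the same analysis.
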